3.3. Benefit/Risk Assessment

More detailed information about the known and expected benefits and risks and reasonably expected adverse events of CAB may be found in the Investigator Brochure [(GlaxoSmithKline Document Number [RH2009/00003/06](#), 2016)].

3.3.1. Risk Assessment

Potential Risk of Clinical Significance	Summary of Data/Rationale for Risk	Mitigation Strategy

Drug Induced Liver Injury (DILIs)
	
A small proportion of participants in the CAB program to date (total exposure approximately 1644 to 01 April 2017) have developed transaminitis (elevated liver transaminases characterized by predominant Alanine aminotransferase [ALT] elevation). In most participants, transient transaminitis was explained by acute hepatitis C infection (majority) and other systemic infections. In a small number of participants, there was not an alternative explanation, suggesting a mild form of DILI without hepatic dysfunction which resolved upon withdrawal of treatment with CAB. Of the four participants with suspected of DILI identified in Phase 2 HIV treatment studies, all were receiving oral CAB.
	
 • Exclusion criteria as described in Section 6.2 will prohibit participants with significant liver impairment based on screening liver chemistry including transaminases (ALT and aspartate aminotransferase [AST]) as well as on prior medical history. Participants with a history of chronic liver disease with ongoing inflammation and/or fibrosis will be excluded. • A 4-week oral lead- in Phase is being implemented in this study, where all participants will receive oral CAB prior to the administration of IM CAB to assess individual tolerance to systemic drug. • Liver transaminases (ALT and AST) will be closely monitored throughout this study (refer to SoA Table 1) and the liver chemistry stopping criteria will be adopted as described in Section 8.1.1 of this protocol. Participants will be withdrawn from CAB treatment where no compelling alternative cause is identified and DILI is suspected. • Participants who develop ALT ≥ 3 times the upper limit of normal (ULN) while on study must consult with Medical Monitor prior to initiation or continuation of CAB LA.

Potential Risk of Clinical Significance	Summary of Data/Rationale for Risk	Mitigation Strategy
Injection Site Reactions (ISRs)	
Clinical experience to date has demonstrated ISRs occur in the majority of participants receiving CAB LA but are generally mild (Grade 1) or moderate (Grade 2) and include events of pain, tenderness, erythema, or nodule formation of several days duration (median duration for individual events <1 week). ISRs may occur more than once in an individual participant receiving multiple injections. Although some Grade 3 ISRs were reported, overall ISRs have been well tolerated and have not to date been associated with an excess of participants withdrawing. None of the ISRs reported to date was serious and no clinically significant complications were reported.
	
 Administration advice will be given to minimize risk of poor administration technique giving rise to injection site reactions. Advice on care, monitoring, natural course, and treatment of ISRs is given in study documentation Advice will be given to participants on care of injection site on day/days immediately post administration, including use of analgesia, compresses where appropriate. Participants will be closely monitored for ISRs particularly for signs of pain, tenderness, infections, erythema, swelling, induration, or nodules (granulomas or cysts) throughout the study.
Hypersensitivity Reactions (HSR)	
Hypersensitivity reactions have been reported as uncommon occurrences with integrase inhibitors, including the closely related compound dolutegravir, and were characterized by rash, constitutional findings, and sometimes, organ dysfunction, including liver injury.
 
While there have been no clinical cases of hypersensitivity to CAB, there is a theoretical risk of systemic or severe hypersensitivity reactions with or without hepatic symptoms associated with use of IM CAB. The long exposures anticipated after IM CAB injection may complicate the management of a drug
	
 The risk of developing a hypersensitivity reaction post administration of IM CAB will be minimized by the use of a 4-week oral lead-in of oral CAB to determine individual tolerance prior to the introduction of IM CAB. Clinical assessments, laboratory tests (including liver transaminases) and vital signs will be performed throughout this study (refer to SoA Table 1). Results from these assessments may aid early detection of HSR. Oral CAB will be withdrawn immediately for

Potential Risk of Clinical Significance	Summary of Data/Rationale for Risk	Mitigation Strategy
	hypersensitivity reaction, were it to occur.	cases with suspected HSR during the oral CAB lead-in phase and would not proceed to the injection phase. Participants in the injection phase would not receive further injections. During oral and IM CAB treatment, any HSR reactions that occur would be managed supportively.
Development of Resistance following discontinuation of CAB LA	Residual concentrations of CAB LA would remain in the systemic circulation of participants who stopped study product (e.g. for tolerability issues or treatment withdrawal) for varying and in some instances prolonged periods (months). Participants discontinuing a LA regimen may be at risk for developing resistance to CAB many weeks after discontinuing injectable therapy were they to become newly infected with HIV.	
 All participants will be provided HIV counseling and testing throughout the study, as well as provision of condoms and lubricant. Additionally, participants will be followed for 56 weeks from the time of the last injection with CAB. Participants who acquire HIV on study will be referred for appropriate care.
Drug-Drug Interactions (DDIs)	
For a complete listing of permitted and prohibited concurrent medications for CAB and CAB LA, refer to Section 7.7
 
CAB and CAB LA should not be co-administered with the following medicinal products, as significant decreases in CAB plasma concentrations may occur (due to UGT enzyme induction), which may result in loss of therapeutic effect of CAB.
 
- the anticonvulsants carbamazepine,
	
 All participants will be informed of prohibited medications throughout the study and updates provided as needed via the informed consent.

Potential Risk of Clinical Significance	Summary of Data/Rationale for Risk	Mitigation Strategy
	
oxcarbazepine, phenobarbital, phenytoin
 
 - the antimycobacterials rifampicin, rifapentine, rifabutin - St John's wort (Hypericum perforatum). 
Oral CAB administration only: Antacid products containing divalent cations (e.g., aluminium, calcium and magnesium) must be taken at least 2 hours before or at least 4 hours after CAB.
 
Participants discontinuing a LA regimen may be at risk for developing DDIs many weeks after discontinuing injectable therapy.
	
Study Procedures		
Risks of ECG pad removal	Participants will be required to have ECG tracings at screening. Some discomfort and rash may occur where the ECG pads are removed.	All ECGs will be conducted by experienced personnel and contact time for the pads on the skin will be kept to a minimum.
Venipuncture as used for blood sample collection	Complications from venipuncture include swelling, bleeding, bruising and infection	
 • These risks will be minimized using current standard of care techniques for venipuncture.

Potential Risk of Clinical Significance	Summary of Data/Rationale for Risk	Mitigation Strategy
Other		
Social Harms	
Participation in the study could lead to social harms that may include loss of privacy, stigmatization, interference with gainful employment, and coercion. Information regarding social harms will be solicited during every 8 week study visits after enrollment in the study and will be recorded in log form on case report forms (CRFs). In addition, social harms may be identified by other study staff, including recruiters, receptionists, nurses, physicians, pharmacist, and others. All social harms will be brought to the attention of the on-site medical officer and reported according to AE reporting guidelines described in Section 12.4. An investigative committee will review social harm reports and determine appropriate follow-up, including modifying the study protocol and/or procedures as necessary. Participants who report social harms will be referred to speak with a social worker and/or a study counselor.
	
 • Participants who report social harms will be referred to speak with a social worker and/or a study counselor.

3.3.2. Other Clinically Relevant Information

Additional details concerning safety observations from clinical studies and for which a causal association has not been established or which are of minimal clinical significance may be found in the Investigator's Brochure (GlaxoSmithKline Document number [RH2009/00003/06](#) IB Version 6)

Adverse Events of Special Interest:

Seizure

Three cases of seizures have occurred in the CAB program cumulatively through 15 May 2016. Two of the cases occurred in HIV uninfected subjects with a prior history of seizure and one case involved a subject in study 200056 with circumstantial and anecdotal evidence of illicit drug use. Overall, there is not convincing evidence that cabotegravir exposure may be causally associated with seizure or with reduction of seizure threshold, due to the low frequency of reports, the confounders present in the cases received to date and lack of any pre-clinical signal or identified plausible mechanism. However, seizure and seizure-like events are considered as AEs of special interest for close monitoring in future studies. Subjects with recent history of, or recent treatment for seizure or determined to have a high risk of seizures, including participants with an unstable or poorly controlled seizure disorder will be excluded from study participation. For further details refer study reference manual (SRM).

All cases of prior seizure history should be discussed with the Medical Monitor prior to enrolment

3.3.3. Benefit Assessment

Participants in the study will benefit from HIV education and prevention counseling efforts. In addition they will receive access to chemoprophylaxis CAB LA which may be effective in reducing HIV acquisition in adherent individuals. Participants will also be screened for sexually transmitted infections (STIs) and referred for treatment, and receive screening for hepatitis B and C.

3.3.4. Overall Benefit: Risk Conclusion

Safety risks in this study are addressed through study design and careful, long term monitoring. Participants in this study will be at risk, though low, for acquisition of HIV on the basis of the inclusion criteria, and could receive a therapeutic benefit, as well as receiving surveillance of HIV acquisition and other sexually transmitted infections, and will have access to additional prevention counseling. The benefit/risk profile for the continued development of the CAB LA injection and oral formulations as mono-therapy in pre-exposure prophylaxis for horizontal HIV transmission in HIV negative patients remains favorable.

4. OBJECTIVES AND ENDPOINTS

Objectives	Endpoints
Primary	
Evaluate the safety and tolerability of the injectable agent, cabotegravir (GSK1265744) long acting (CAB LA) injectable (600 mg dose administered every 4 weeks for 2 doses followed by every 8 weeks for 3 doses) through Week 5-41 in HIV-1 uninfected Chinese men.	Safety and tolerability parameters, including adverse events, clinical laboratory tests, study withdrawals due to AEs, vital signs assessments, and evaluation of injection site reactions (ISRs).
Evaluate the plasma pharmacokinetics of CAB following repeat oral administration (Day 1 to Week 4) and CAB LA IM injections throughout the Injection Phase (Weeks 5-41).	Plasma CAB PK parameters following repeated once daily oral administration (Day1-Week 4) include (as permitted by the data): C_{τ} , $AUC(0-\tau)$, C_{max} , t_{max} , CL/F , V_{ss} , $t_{1/2}$, and λ_z . Plasma CAB PK parameters following CAB LA IM administration (Week 5-Week 41) include (as permitted by the data): C_{τ} , $AUC(0-\tau)$, C_{max} and t_{max} .
Secondary	
Evaluate the plasma pharmacokinetics of CAB LA through the Injection and Long-term Follow-up Phases (Week 5-89)	Plasma CAB PK parameters following CAB LA IM administration (Week 5 - Week 89) as permitted by the data including C_{τ} , $AUC(0-\tau)$, C_{max} , t_{max} , CL/F , V_{ss} , $t_{1/2}$, and λ_z .
Evaluate the safety and tolerability of oral CAB in HIV uninfected Chinese men during the oral lead-in Phase (Day 1 to Week 4)	Safety and tolerability parameters, including adverse events, study withdrawals due to AEs, vital signs assessments and clinical laboratory assessments.
Evaluate the acceptability of CAB LA injections through 41 weeks.	Injection discontinuation rate, the number and severity of ISRs and additional acceptability measures.
Explore concentration-effect relationships for various safety and tolerability parameters if relevant.	Evaluation of relationships between significant safety and tolerability parameters and CAB PK may be explored.

AE: Adverse events, $AUC(0-\tau)$: Area under the plasma concentration time curve over the dosing interval, C_{τ} : Concentration at the end of the dosing interval, C_{max} : Maximum observed concentration, T_{max} : Time of occurrence of C_{max} , τ : Dosing interval, λ_z : Apparent terminal phase rate constant, CL/F : Oral clearance, V_{ss} : volume of distribution at steady state, $t_{1/2}$: Terminal absorption elimination half-life.

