2. SCHEDULE OF ACTIVITIES (SOA)

Table 1 SCHEDULE OF ACTIVITIES^a

Clinical Assessments	Screening ^a	Oral Phase ^m		Injection Phase												Follow-up Phase & Final Visit	
		Day 1	Day 28 (Week 4)	Day 35 (Week 5) Injection 1	Day 42 (Week 6)	Week 9 Injection 2	Week 10	Week 17 Injection 3	Week 18	Week 25 Injection 4	Week 26	Week 33 Injection 5	Week 34	Week 37	Week 41	Week 53, 65, 77	Week 89
Written informed consent	X																
Inclusion/Exclusion criteria ^b	X																
Demographic information	X																
Full physical exam/medical history ^c	X																X
Brief physical exam		X	X	X	X	X	X	X	X	X	X	X	X	X	X		
Height/weight/BMI ^d	X																X
Medication/drug/alcohol history	X																
HIV counseling	X	X	X	X	X	X	X	X	X	X	X	X	X	X	X	X	X
Offer condoms and lubricant	X	X	X	X	X	X	X	X	X	X	X	X	X	X	X	X	X
Dispense oral study medication (with counseling) ^e		X															
Drug accountability (pill counts)		X	X														
CAB LA Injection (with counseling)				X		X		X		X		X					
HIV-PrevTSC ^f							X										
Oral phase diary card		X															

Clinical Assessments	Screening ^a	Oral Phase ^m		Injection Phase												Follow-up Phase & Final Visit	
		Day 1	Day 28 (Week 4)	Day 35 (Week 5) Injection 1	Day 42 (Week 6)	Week 9 Injection 2	Week 10	Week 17 Injection 3	Week 18	Week 25 Injection 4	Week 26	Week 33 Injection 5	Week 34	Week 37	Week 41	Week 53, 65, 77	Week 89
ISR AE Diary ^g				X		X		X		X		X					
AE		X	X	X	X	X	X	X	X	X	X	X	X	X	X	X	X
SAE review (SAE will be collected from the signing of ICF)	X	X	X	X	X	X	X	X	X	X	X	X	X	X	X	X	X
Concomitant medication check		X	X	X	X	X	X	X	X	X	X	X	X	X	X	X	X
Vital signs ^h	X	X		X	X	X	X	X	X	X	X	X	X	X	X	X	X
Qualitative HIV RNA by NAAT ⁱ	X																
HIV PoC test ^j	X	X		X		X		X		X		X			X	X	X
ECG ^k	X																
HbsAg and HbsAb, HCV Antibody	X																
Hematology/Chemistry testing	X	X	X	X	X	X		X		X		X			X		X
Urinalysis	X														X		
Urine drug screen	X																
Urine chemistry		X															
Urine screen for Chlamydia and gonorrhea	X																
Liver Chemistry Tests ^l																X	
Fasting lipid profile		X													X		
Coagulation testing	X														X		

Clinical Assessments	Screening ^a	Oral Phase ^m		Injection Phase												Follow-up Phase & Final Visit		

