		Day 1	Day 28 (Week 4)	Day 35 (Week 5) Injection 1	Day 42 (Week 6)	Week 9 Injection 2	Week 10	Week 17 Injection 3	Week 18	Week 25 Injection 4	Week 26	Week 33 Injection 5	Week 34	Week 37	Week 41	Week 53, 65, 77	Week 89	
TRUST for Syphilis screen	X																	
Plasma for CAB concentration ^{m,n,o}			X ^m	X	X	X	X	X	X	X	X	X	X	X	X	X	X	X
Plasma storage sample ^p	X	X	X	X	X	X	X	X	X	X	X	X	X	X	X	X	X	X

AE: Adverse events, BMI: Body mass index, CAB: Cabotegravir, CAB LA: Cabotegravir long-acting, ECG: Electrocardiogram, HbsAg: Hepatitis B surface antigen, HIV: Human Immunodeficiency Virus, HCV: Hepatitis C Virus, ISR: Injection site reactions, SAE: Serious adverse event, HIV-PrevTSQc: HIV-Prevention Treatment Satisfaction Questionnaire (change): TRUST: Tolidine Red Unheated Serum Test, RNA: Ribonucleic acid.

- Screening (including drug screen) is to be performed within 30 days of the first dose in the Oral Phase of the study. See [Appendix 2](#)
- Inclusion/exclusion criteria will be fully assessed at the Screening visit. Changes between the screening visit and the Day 1 visit should be assessed to ensure eligibility, including additional assessments performed at Day 1.
- A full physical exam will be performed at Week 89.
- Weight will be collected at Screening and at Week 89. Height and BMI will be collected at Screening only.
- Oral phase consists of 28 days with a 7 day washout period between Day 28 (last oral dose) and Day 35 (first injection visit).
- HIV-PrevTSQc: HIV-Prevention Treatment Satisfaction Questionnaire (change) will be given at Week 10 only (after 2nd injection).
- ISR AE 7 Day Post Injection Diary will be distributed at the injection visit at Week 5, 9, 17, 25 and 33 and returned to the clinic at weeks 6, 10, 18, 26, and 34. For participants having ISR on the last day of week 5, 9, 17, 25 and 33, additional ISR AE Weeks 2 – 12 Post Injection Diary will be distributed at weeks 6,10, 18, and 26,34. Participants will be asked to bring the diary to each clinic visit.
- Vital sign measurements will be performed following 5 minutes of rest.
- Qualitative HIV Nucleic Acid Amplification Testing (NAAT) will be performed at Screening. See [Appendix 9](#) for the HIV testing algorithm at screening, Day 1 and during the course of the study.

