9.4. Safety Assessments

Planned time points for all safety assessments are provided in the SoA (Section 2).

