9.4.1. Physical Examinations

- A complete physical examination will include, at a minimum, assessment of the (Skin, Cardiovascular, Respiratory, Gastrointestinal and Neurological) systems. Height and weight will also be measured and recorded.
- A brief physical examination will include, at a minimum assessments of the (Skin, lungs, cardiovascular system, and abdomen [Liver and spleen]).
- Investigators should pay special attention to clinical signs related to previous serious illnesses.

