8.2. Safety and Tolerability Analyses of Oral CAB

The safety and tolerability analyses of oral CAB will include Grade 2 or higher clinical and laboratory events occurred during the oral phase. Analysis time frame is from the first date of taking oral CAB tablet to the date right before the first CAB LA injection. For subjects who withdraw treatment from the oral phase, the analysis will include all safety and tolerability assessments from the first date of taking oral CAB tablet up to the date of last study visit.

Safety endpoints including adverse events, laboratory test, vital signs, and death will be analysed. The same analysis approaches will be conducted as in the primary analysis, but with different time frame.

[Table 13](#) provides an overview of the planned analyses, with full details of data displays being presented in [Appendix 14](#): List of Data Displays.

Table 13 Overview of Planned AE, LB, VS, and Death Analyses

Display Type	Data Displays Generated						
	Stats Analysis			Summary		Individual	
	T	F	L	T	F	F	L
AE Analyses							
All AEs				Y			Y
Grade 2 or higher AEs				Y			Y
SAEs				Y			Y
AE leading to treatment discontinuation or study withdrawal				Y			Y
Drug-related AEs				Y			
Drug-related SAEs				Y			
Drug-related Grade 2 or higher AEs				Y			
Common AEs				Y			
Common non-serious AEs				Y			
Common Grade 2-4 AEs				Y			
Common drug-related Grade 2-4 AEs				Y			
Laboratory Tests							
Grade 2 or higher laboratory events				Y			
Clinical Chemistry				Y			Y
Hematology				Y			Y
Fasting Lipid Profile				Y			Y
Urinalysis				Y			Y
Coagulation Profile				Y			Y
Other lab data including local lab							Y
Vital Sign Analysis							
Vital Signs				Y			Y
Death Analysis							
Death							Y

NOTES:

- T = Table, F = Figure, L = Listing, Y = Yes display generated.
- Stats Analysis = Represents TFL related to any formal statistical analyses (i.e. modelling) conducted.
- Summary = Represents TFL related to any summaries (i.e. descriptive statistics) of the observed raw data.
- Individual = Represents FL related to any displays of individual subject observed raw data.

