10.4. Appendix 4: Study Phase and State

10.4.1. Treatment Phases

Assessments and events will be classified according to the time of occurrence relative to the start date of study treatment.

Treatment Phase	Definition
Screening Phase	Date < Date of first Oral CAB
Oral Phase	Date of First Oral CAB <= Date <= Date of First CAB LA Injection -1 day; for subjects who discontinued before receiving CAB LA Injection, the end date of the oral phase is the date of last study visit.
Injection Phase	Date of First CAB LA Injection <= Date <= 8 weeks after Last CAB LA Injection
Follow-up Phase	Date > 8 weeks after Last CAB LA Injection

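### Vital signs are part of the oral lead-in safety endpoint, but none are scheduled between Day 1 and Week 5

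*Protocol*

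**What the plan says.** **Endpoint.** Protocol Section 4 (and the Synopsis) gives the secondary endpoint for the oral lead-in, Day 1 to Week 4, as "Safety and tolerability parameters, including adverse events, study withdrawals due to AEs, vital signs assessments and clinical laboratory assessments".

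**Analysis.** SAP 8.2 carries this forward: "Safety endpoints including adverse events, laboratory test, vital signs, and death will be analysed". It applies the methods of the primary analysis over the oral time frame. For vital signs, SAP 7.1.4 defines those methods as change from baseline by visit plus a shift table. SAP Table 13 has a vital-signs row for the oral phase.

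**Schedule.** In Protocol Table 1 the row opens "Vital signs ^h X X X". Aligned with the column headings, those three marks are Screening, Day 1 and Week 5; the Day 28 (Week 4) cell between the second and third is empty. SAP Table 21 has the same blank in both versions of the plan contained in the SAP document. Protocol 9.4 makes the schedule the source of timing: "Planned time points for all safety assessments are provided in the SoA (Section 2)".

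**Phase boundary.** A schedule footnote states: "Oral phase consists of 28 days with a 7 day washout period between Day 28 (last oral dose) and Day 35 (first injection visit)". SAP 10.4.1 ends the oral phase the day before the first injection and defines the injection phase as "Date of First CAB LA Injection <= Date <= 8 weeks after Last CAB LA Injection".

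**The concern.** A named component of an endpoint, with an analysis planned for it, has no scheduled measurement in the period it is meant to describe. The lead-in exists to check tolerance of oral drug before a long-acting injection is given. The hypersensitivity row of Protocol 3.3.1 adds that "Clinical assessments, laboratory tests (including liver transaminases) and vital signs will be performed throughout this study", which the schedule does not deliver between Day 1 and Week 5. A reader of the final report would expect an on-tablet vital-sign result, and the plan as written gives no scheduled data for one.

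**Working it through.** No sample-size or power figure is involved. The check is a cell-by-cell count of the schedule against the SAP's date rule.

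1. **Column alignment.** Table 1 has 17 visit columns and the vital-signs row has 17 cells. Sixteen are marked; the only blank is Day 28 (Week 4). The brief physical exam, haematology/chemistry and concomitant-medication rows also have 17 cells and do carry a mark at Day 28. The blank is therefore not a shifted column. SAP Table 21 gives the same result in both versions.

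2. **Scheduled measurements after Day 1 and before Day 35.** Day 28 is the only schedule visit in that interval, and it is blank for vital signs. Count: 0.

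3. **Other scheduled sources.** Protocol 9.4.1 says of the exam done at Day 28: "A brief physical examination will include, at a minimum assessments of the (Skin, lungs, cardiovascular system, and abdomen [Liver and spleen)". Vital signs are not in that minimum content. The intensive PK schedule (Protocol Table 2) lists only dosing and plasma samples.

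4. **Day 1.** Under SAP 10.5.2.1, baseline is the last value before the first dose, so Day 1 (or Screening) serves as baseline. The schedule does not say whether Day 1 vital signs precede the tablet. If they follow it, they describe the first day only, not four weeks of dosing.

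5. **Week 5.** Day 35 − Day 28 = 7 days after the last tablet. The measurement falls on the first injection date, so SAP 10.4.1 assigns it to the injection phase. It exists only for men who reach that visit. Protocol 5.2 plans about 48 entering the oral phase and about 40 entering the injection phase: 48 − 40 = about 8 who may have no Week 5 value.

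6. **Result.** Scheduled on-treatment oral-phase measurements per participant: 0 as written; 1 if Day 28 is marked. Across the planned cohort that is 48 × 0 = 0 as written, against up to 48 × 1 = 48 with the mark, less any man who leaves before Day 28.

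7. **Related rows of SAP Table 13.** The table also lists oral-phase lipid, coagulation and urinalysis summaries. Protocol Table 1 schedules lipids at Day 1 and Week 41, and coagulation and urinalysis at Screening and Week 41. None has a scheduled post-baseline value in the oral phase.

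**The case against.** Several stronger readings are tempting, and the other side is right to resist them.

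- **That a separate oral-phase table would be printed with n = 0 and misread as no change.** SAP Appendix 14 lists no such table. It lists Table 2.24 (change from baseline) and Table 2.25 (shifts), both on the Safety population. By visit, Table 2.24 would lack a Week 4 row and would show Week 5. Table 13 is an overview that refers to Appendix 14 for detail.
- **That nobody could have any post-baseline value.** Protocol 8.2.1 asks for early-termination procedures, although the schedule has no column saying what they contain. SAP 8.2 includes assessments up to the last study visit for men who withdraw during the oral phase. Under SAP 10.4.1 a man who attended Week 5 but was not injected would have that value counted as oral phase. Unscheduled values may exist, although SAP 10.5.3 lists them without summarising them.
- **That the decision to proceed to injection, or detection of hypersensitivity, depends on the missing measurement.** Day 28 has adverse-event review, a brief exam, haematology and chemistry. Protocol 3.3.1 says only that the results may help early detection, and names vital signs as one of three kinds of assessment.
- **That the lipid, coagulation and urinalysis rows are further failed endpoints.** The oral endpoint names clinical laboratory assessments in general, and Day 28 haematology and chemistry supply them.

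All four limits stand. None of them provides a scheduled on-tablet vital sign, so the mismatch between endpoint, schedule and SAP remains.

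**Conclusion.** The inconsistency is real and narrow. Vital signs are a stated component of the oral lead-in endpoint with a planned analysis, and the schedule provides 0 on-treatment measurements for it. Week 5 is not a like-for-like substitute: it is post-washout, limited to men who reach that visit, and assigned to the injection phase for those injected.

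This rests on two assumptions: that the blank is intended as printed (it is the same in the protocol and in both SAP versions), and that Day 1 vital signs act as baseline.

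The consequence is modest. One of four listed components of a secondary endpoint is affected, in a single-arm study with no formal hypotheses. The primary injection-phase vital-sign endpoint is fully scheduled. It should be corrected, but it does not threaten the study's main conclusions.

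**What to change.** **If Day 28 visits are still to come:** mark vital signs at Day 28 (Week 4) in Protocol Table 1 and SAP Table 21. Under Protocol 9.4.5 this means five minutes' rest and three blood-pressure and pulse readings, with temperature and respiratory rate, at a visit participants already attend. No visit is added. The change needs ethics approval as a protocol amendment (Appendix 3).

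**If those visits have passed:** state in SAP 2.1 and 8.2 that on-tablet vital signs were not measured. Then either remove them from the oral-phase analysis, or report the Week 5 value labelled as post-washout. This costs only SAP wording.

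**Minor clean-up in either case:** label the oral-phase lipid, coagulation and urinalysis rows of SAP Table 13 as not assessed on oral cabotegravir.
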